2.3 Benefit/Risk assessment

Generalized MG is a rare, debilitating, chronic autoimmune disease driven by, in large part, IgG autoantibodies that target neuromuscular junctions (NMJs). Most current treatment approaches are not targeted treatments to the specific underlying pathology of IgG autoantibody formation, but rather they produce a broad cascade of immune suppression, which results in undesirable side effects such as those seen with high-dose chronic steroid use. Many treatments of choice often require invasive, expensive, and time-consuming inpatient procedures such as PEX, or intravenous (IV) administration of immunoglobulins at a healthcare facility.

Rozanolixizumab represents an innovative, SC anti-FcRn monoclonal antibody that may provide a novel and specific therapeutic approach for the treatment of study participants with MG. Data show that rozanolixizumab markedly lowers serum IgG and IgG autoantibody levels in study participants with generalized MG. The completed Phase 2 study MG0002 established supportive evidence of efficacy for the treatment of MG, achieving significant and clinically meaningful improvements to Day 29 in MG-ADL with rozanolixizumab ██████████ compared with placebo ($p=0.036$). Repeated administrations of rozanolixizumab were generally well tolerated, with an acceptable safety profile and in line with SC dosing in the Phase 1 program and the safety profile observed in TP0001.

The potential risks associated with SC administration of rozanolixizumab are gastrointestinal (GI) disturbances, headaches, infusion/hypersensitivity reactions, infections, potential effects on immunizations, effects on the kidney, and metabolic effect of FcRn on albumin. These risks can be mitigated by careful monitoring, exclusion of at-risk study participants, and appropriate protocol withdrawal and stopping criteria. Additionally, protocol guidance for management of GI disturbances, severe headaches, and infusions/hypersensitivity reactions is also provided as well as expedited reporting requirements of adverse events of special monitoring (AESMs).

More detailed information about the known and expected benefits and risks and reasonably expected adverse events (AEs) of rozanolixizumab may be found in the IB.

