4.3 Justification for dose

The dose regimen for rozanolixizumab in MG0004 will be the same one that is used in MG0003 and MGC003 (see Section 4.1 for details of dosing according to weight). The fixed dosing units were introduced to support the potential for study participant self-injection in a home setting and doses have been defined to reach PD effect on IgG levels throughout a weight range that is similar to weight-based dosing.

The proposed doses and regimen of rozanolixizumab in MG0003 were based on the results from first-in-human study UP0018, alongside the efficacy and safety data from the MG Phase 2 study (MG0002), and safety and tolerability data from TP0001. UP0018 evaluated the effect of a single dose of rozanolixizumab (administered at doses of [REDACTED] as IV or SC infusions) in healthy study participants. The mean absolute decreases in IgG and mean percent change from Baseline IgG were greater in the active dose groups compared with placebo-treated study participants, and rozanolixizumab treatment was tolerated with an acceptable safety profile.

MG0002 evaluated the effect of repeated doses of rozanolixizumab (administered at doses of [REDACTED] as SC infusions) in study participants with generalized MG. Significant improvements in day-to-day functioning (measured by change from Baseline to Day 29) were observed. In general, responder rates for quantitative myasthenia gravis (QMG) score, MG-C score, and MG-activities of daily living (ADL) score were higher for the rozanolixizumab [REDACTED] group than the placebo group. Serum total IgG concentrations and AChR autoantibodies rapidly decreased from Baseline in the rozanolixizumab [REDACTED] group, with a mean nadir of 3.3g/L for total IgG (~70% reduction from Baseline). Overall, repeated administrations of rozanolixizumab were generally well tolerated, with an acceptable safety profile.

TP0001 indicated that rozanolixizumab dose higher than [REDACTED] was tolerated with an acceptable safety profile after multiple [REDACTED] and [REDACTED] doses.

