6.6 Dose modification

Study participants will be allowed to switch dose arms for tolerability and efficacy reasons, as well as bodyweight changes at the discretion of the Investigator after the first dose of rozanolixizumab. However, when possible, the dose assigned at randomization should be maintained for at least 6 weeks, unless a dose modification is required earlier for tolerability or efficacy reasons. If a dose adjustment is made, the Investigator should encourage study

participants to stay on the modified dose for at least 6 weeks, unless further dose adjustments or discontinuation of study medication is required for the safety of the study participant.

Study participants who experience any AEs that meet the study medication discontinuation criteria (Section 7.1 and Section 0) should have rozanolixizumab discontinued. Study participants in the [REDACTED] cohort who experience a possibly related toxicity other than those that met the study drug discontinuation criteria as defined in Section 7.1 and Section 0 are allowed to switch to [REDACTED] at the Investigator's discretion. Recommended dose modifications due to toxicities may include (but not exclusive):

- Moderate to severe headaches that are considered to be related to rozanolixizumab (Section 10.20.1)
- Moderate to severe GI disturbances that are considered to be related to rozanolixizumab
- Moderate to severe toxicities (\geq Grade 2 as defined by CTCAE, version 5) for which rozanolixizumab cannot be excluded as a cause
- Recurrent hypogammaglobulinemia with a serum total IgG $<2\text{g/L}$

The date and reason for dose change of rozanolixizumab is to be recorded on each study participant's eCRF.

If any safety concerns are identified in MG0003 (ie, as recommended by the IDMC), or if one of the dose arms is determined to be futile and is discontinued in MG0003, corresponding changes may be made in the MG0004 dosing scheme. A study participant on a dose that was discontinued will switch doses immediately.

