7.1.4 Temporary IMP discontinuation

Study participant ***must be*** TEMPORARILY discontinued from the IMP if any of the following events occur:

1. The study participant develops an event of hypogammaglobulinemia with a serum total IgG of <1g/L irrespective of infection. When the IgG level reaches ≥ 2 g/L, the study participant may be allowed to continue treatment with IMP (see Appendix 22; Section 10.22.3).
2. In the event of confirmed COVID-19 infection. IMP may be restarted if clinically appropriate when signs and symptoms have resolved.

Study participants ***may be TEMPORARILY discontinued from the IMP*** if the following events occur:

1. The study participant develops a non-serious persisting or recurrent infection with serum total IgG level between ≥ 1 and <2g/L. Upon resolution of infection and the IgG returning to level of ≥ 2 g/L, the study participant may be allowed to resume treatment with the IMP (see Appendix 22; Section 10.22.3).
2. In the event of suspected (eg, signs/symptoms such as fever, cough, shortness of breath) COVID-19 infection, or known exposure sufficient to necessitate testing or self-imposed quarantine, IMP may be restarted when clinically appropriate if:
 - a. COVID-19 test is negative, and signs and symptoms have resolved.
 - b. If test is not available, resolution of signs and symptoms and 14 days have passed since initial presentation of the clinical signs/symptoms.
 - c. If asymptomatic, 14 days have passed since known exposure.

The investigator should discuss with sponsor's study physician prior to re-initiating the IMP. As appropriate, virtual assessments could continue (eg, AE collection, PRO assessments).

If IMP treatment is resumed, continue the next dose as previously scheduled. No "make up" dose is permitted. The participant should subsequently follow the visit schedule as described in the protocol and the eCRF should be completed accordingly.

The study participant should follow the visit schedule as described in the protocol and the eCRF completed accordingly.

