10.20.3 Management of infections and hypogammaglobulinemia

Study participants who have signs or symptoms of any infection should be monitored closely and managed according to local guidelines. This may include tests for specific organisms if clinically indicated.

Study participants **MUST discontinue IMP AND move** into **the SFU Period** if any of the following events occur: Study participant has a serious infective episode requiring hospitalization or IV antibiotic therapy (ie, bacteremia or sepsis, bacterial meningitis, osteomyelitis or septic arthritis, bacterial pneumonia, or visceral abscess).

To maintain the study integrity, IgG level will remain blinded to the study sites and the UCB study team for the first 4 weeks of the study. To ensure patient safety, serum IgG level will be monitored by an independent medical monitor external to UCB including signs and symptoms of infection and associated laboratory parameters. The IMP may be temporarily discontinued as requested by the independent medical monitor when deemed appropriate.

In the event of a non-serious infection, the Benefit-Risk of continuing treatment with IMP must be carefully evaluated by the Investigator in collaboration with the medical monitor. Treatment may be temporarily discontinued for the study participant who develops a non-serious persisting or recurrent infection with a serum total IgG level between $\geq 1\text{g/L}$ and $< 2\text{g/L}$. Upon resolution of infection and the IgGs returning to the level of $\geq 2\text{g/L}$, the study participant may be allowed to resume treatment with the IMP. Ad hoc assessment can be performed to monitor the recovery of IgG levels.

Treatment **MUST** be temporarily discontinued for the study participant who develops an event of hypogammaglobulinemia with a serum total IgG of $< 1\text{g/L}$ irrespective of infection. When the IgG level reaches $\geq 2\text{g/L}$, the study participant may be allowed to continue treatment with IMP.

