8.2.3 Adverse events of focus

Rozanolixizumab adverse events of focus (AEOF) include the following categories:

- Headaches
- Gastrointestinal disturbances
- Hypersensitivity reactions
- Anaphylactic reactions
- Injection site reaction
- Infusion reaction
- Infections
- Opportunistic infections
- Reductions in albumin and plasma proteins
- Effects on the kidney
- Drug related hepatic disorders
- Effects on lipids

1. The number and percentage of study participants who experience each category of the AEOF will be summarized by most recent dose level prior to onset of the AEOF and RLZ total treatment group. The following summaries will be presented by SOC, HLT, and PT:

- AEOF
- Serious AEOF
- AEOF by relationship
- AEOF by maximum intensity (mild, moderate and severe)

2. Additionally, the summaries for the AEOF headache and gastrointestinal disturbances in Treatment Period by intensity will be presented separately by most recent dose level and RLZ total.

3. Graphs for AEOF headache in Treatment Period by time of onset (relative to infusion), severity, causality and duration for each study participant will also be provided.

A by-subject listing of all AEOF by category (as listed above) will be provided by treatment group and participant. Most recent dose will be presented in listing even when the AE start date is partial. Further details related to the statistical analysis of the above mentioned treatment-emergent AEOFs are provided in [Section 13.8](#).

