		
The SPs reviews the context of all of a subject's data (AEs and possibly other) and concludes individually. Indicators of relevant cases may be e.g. repetitive occurrences, conjunction of other events or findings considered relevant.
 
All subjects with a case-by-case PT reported that has been confirmed by the SPs to be an OI will be summarized as such in the stand-alone table, along with all of the events identified in Step 1 of this process. [CQ99NAM= 'Opportunistic Infection – Adjudicated']
 
The timing and frequency of Step 2 should be outlined and agreed to by the study team at the beginning of the study. It is suggested that this process be executed multiple times throughout the course of the study, more frequently in the weeks leading up to database lock, and one final time immediately prior to database lock.
 
Following the initial review of case-by-case events, subsequent reviews will be based on the cumulative set of case-by-case events present in the database at each time point of spreadsheet creation.
 
Physician decisions from previous runs should be retained in each subsequent run. The final run of the spreadsheet, with all SP decisions on the full set of case-by-case events, will be archived at the conclusion of the study analysis prepared for agency submission.

9	Reductions in albumin and plasma proteins	TEAEs with PT='Blood albumin decreased' or PT='Protein albumin ratio' or LLT='Plasma protein abnormal' or LLT='Proteins serum plasma low'
10	Effects on the kidney	TEAEs in SMQ= 'Acute renal failure'
11	Drug related hepatic disorders	TEAEs in SMQ='Drug related hepatic disorders - comprehensive search'
12	Effect on lipids	TEAEs with PT= 'Blood cholesterol increased' or PT= 'Low density lipoprotein increased' or PT= 'Blood triglycerides increased' or PT= 'Hypercholesterolaemia' or PT= 'Hypertriglyceridaemia' or PT= 'Hyperlipidaemia' or PT= 'Dyslipidaemia' or PT= 'Lipids increased'

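### The adverse-event-of-focus category for albumin and plasma protein reductions selects only four laboratory-type terms, so it would undercount the events it is named for

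*SAP*

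**What the plan says.** SAP 8.2.3 lists twelve AEOF categories, one of them "Reductions in albumin and plasma proteins". Each category gets four summaries (all, serious, by relationship, by maximum intensity) by most recent dose, plus a listing. SAP 13.8 gives the selection rules. Row 9 reads: "TEAEs with PT='Blood albumin decreased' or PT='Protein albumin ratio' or LLT='Plasma protein abnormal' or LLT='Proteins serum plasma low".

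Row 12, on lipids, is built differently. Beside laboratory terms it lists diagnosis terms such as "PT= 'Hypercholesterolaemia".

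The protocol treats low immunoglobulin as an event with a name:

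- 7.1.4, as a reason for a temporary hold: "The study participant develops an event of hypogammaglobulinemia with a serum total IgG of <1g/L irrespective of infection".
- 6.6, among the recommended reasons for dose modification: "Recurrent hypogammaglobulinemia with a serum total IgG" below 2 g/L.
- 10.20.3, where the hold rule reappears for a participant who "develops an event of hypogammaglobulinemia with a serum total IgG of" less than 1 g/L.
- 6.8, on prolonged cases after treatment stops.

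Protocol 10.3.3 tells investigators to record a diagnosis as the AE in preference to its signs and symptoms, where possible.

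**The concern.** A category named for reductions in albumin and plasma proteins should collect an event reported as hypoalbuminemia, hypoproteinemia or hypogammaglobulinemia. Row 9 contains none of these. It also contains no term for decreased immunoglobulin G, although IgG is the plasma protein the drug is designed to lower: Protocol 4.3 reports Phase 2 results "with a mean nadir of 3.3g/L for total IgG (~70% reduction from Baseline".

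An AEOF category exists to give one grouped participant count for a topic, with its serious, related and severe breakdowns. If the search leaves out the usual diagnosis terms, the row can be close to zero while such events are being reported. A reader would take that as a finding about the drug when it only reflects the term list. Long-term safety is this study's primary objective, so the grouped safety tables will be read closely.

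**Working it through.** No figure in the plan needs reproducing. The check compares term lists and then sizes the gap under stated assumptions.

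**1. Row 9 term by term.** There are two preferred terms and two lower level terms.

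| Row 9 term | Laboratory result or diagnosis | Names an immunoglobulin? |
|---|---|---|
| Blood albumin decreased | laboratory | no |
| Protein albumin ratio | laboratory | no |
| Plasma protein abnormal | laboratory | no |
| Proteins serum plasma low | laboratory | no |

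Diagnosis terms: 0 of 4. Immunoglobulin terms: 0 of 4.

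**2. Row 12 on the same reading.** It has eight preferred terms. Four are laboratory-type (cholesterol, low density lipoprotein, triglycerides and lipids increased). Four are diagnoses (hypercholesterolaemia, hypertriglyceridaemia, hyperlipidaemia, dyslipidaemia). So 4 of 8 are diagnoses, against 0 of 4 in row 9. Two things follow. The table has no general rule of using laboratory terms only. And the dictionary holds a raised laboratory value and its diagnosis as separate terms, so a search on one does not bring in the other.

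**3. The other AEOF rows.** None of the twelve category titles refers to immunoglobulins or hypogammaglobulinemia. Some rows (hypersensitivity, anaphylaxis, kidney, liver) use standardised queries whose contents are not in the documents. A protein or albumin term might enter one of those, but it would then be counted under that other title. The adverse events of special monitoring (Protocol 8.3.7) do not include it either.

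**4. How events would be reported.** Protocol 10.3.3 favours a diagnosis over component signs and symptoms; row 9 accepts only laboratory-type terms. The reporting instruction and the search therefore pull apart. For IgG the gap does not depend on this, because row 9 has no term specific to IgG even in laboratory form.

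**5. Where the events do appear.**

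| Output | SAP section | What it shows |
|---|---|---|
| TEAEs by SOC, HLT and PT, including serious, by relationship, by intensity, leading to temporary withdrawal, requiring dose change | 8.2.2 | each event under its own PT |
| Markedly abnormal values, any visit, by most recent dose | 8.3, 13.7 | IgG ≤1 g/L; albumin <20 g/L |
| Total IgG by visit, maximum change, individual plots | 10.2.1 | by first dose received |
| Data for the IDMC reviews | 4.4.2 | includes total IgG |

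**6. Size.** SAP 3.9 gives a maximum of 240 participants. The documents state no rate for these events, so a range is assumed:

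- 1%: 240 × 0.01 = 2.4, about 2
- 5%: 240 × 0.05 = 12
- 10%: 240 × 0.10 = 24

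If these events code outside the four terms, row 9 counts none of them.

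**The case against.** The strongest reply is that nothing is hidden. Step 5 shows the events under their own preferred term in the general TEAE tables, with the same serious, relationship and intensity splits, and low IgG counted from laboratory data. For infections (row 7) the SAP itself says the general tables suffice. AEOF is a supplementary grouping: the primary endpoints are all TEAEs and TEAEs leading to permanent withdrawal. Protocol 10.20.3 also keeps IgG results from sites for the first four weeks, so the laboratory count is the better measure of low IgG. All of this stands, and it confines the error to the AEOF grouping. It does not remove it. Row 7 covers a whole system organ class and says openly that it is reported elsewhere; row 9 is programmed, and its title promises more than its terms deliver.

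A second reply is that row 9 was meant for albumin, since the potential risks in Protocol 2.3 include a "metabolic effect of FcRn on albumin" and do not list hypogammaglobulinemia. But the title also covers plasma proteins, and even for albumin the row omits the diagnosis term.

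Third, the dictionary and the sponsor's AEs-of-focus document are not available here, so the coding cannot be confirmed. That is fair. Row 12 supports the inference without proving it.

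A reader might go further and infer that the plan conceals the drug's main pharmacological risk, or that it excludes the very term sites are told to use. The documents support neither. Lowering IgG is the intended effect, Protocol 2.3 ranks no risk as the main one, and Protocol 10.20.1 names headache as the most commonly reported adverse drug reaction. Protocol 6.6, 7.1.4 and 10.20.3 are management rules; they do not tell sites how to word an AE.

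**Conclusion.** Row 9 is incomplete as written. The AEOF tables for this category (overall, serious, by relationship, by intensity) would undercount the reductions the category is named for, both albumin and protein diagnoses and all immunoglobulin events, including one the protocol manages by name. The effect is limited to this grouping; overall TEAE reporting and the laboratory outputs are intact, and no listed endpoint changes.

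The number missed is unknown. The 2 to 24 participants in step 6 rest on an assumed 1 to 10% and on the maximum enrolment of 240, and would be absent from one category, not from the safety report. The conclusion also assumes that hypoalbuminemia, hypoproteinemia, hypogammaglobulinemia and decreased immunoglobulin G code to terms other than the four listed, as the structure of row 12 suggests.

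**What to change.** In SAP 13.8, row 9, add the terms to which hypoalbuminemia, hypoproteinemia, hypogammaglobulinemia and decreased immunoglobulin G code in the MedDRA version in use, pairing laboratory and diagnosis terms as row 12 does. Put the same list in the sponsor's AEs-of-focus document, which SAP 13.8 cites as the source of the criteria, so that the MG studies stay aligned; SAP 14.1 gives that alignment as the reason for the current definitions.

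Two additions are optional. Albumin and immunoglobulin events could be shown separately within the category, so that an intended effect on IgG does not mask an albumin signal. A count of participants with total IgG below 2 g/L could be added, because the protocol refers to that level and the markedly abnormal table stops at 1 g/L.

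The cost is a change to a term list and a matching update in the other MG studies. The category count will be higher, and pooled tables need the same list throughout. No dose, threshold or management rule changes.

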14 AMENDMENT(S) TO THE STATISTICAL ANALYSIS PLAN

14.1 Amendment 1

Rationale for the amendment

This amendment is to apply following changes:

- Adverse event summaries to be consistent with MG0003
- Update definitions of ADA participant categories, and update related analyses
- Minor cosmetic changes

Modifications and changes

Section # and Name	Description of Change	Brief Rationale
General	Added RLZ total to summary tables	To be consistent with MG0003
General	Minor administrative, formatting, and typographical changes have been made.	Updated to provide clarity and be consistent with remainder of SAP.
3.3 Definition of Baseline values	Modified general definition of Baseline values and added Baseline definition for anti-drug antibody.	To consider actual assessment time and add more accurate definition for ADA considering MG0003 treatment effect
3.8 Coding dictionaries	Updated MedDRA and WHODD version	Newer versions were released
4.9 Examination of subgroups	The stratification factors MuSK(+/-) and AChR(+/-) in the subgroup analysis were changed to be based on the values from MG-specific autoantibody assessment taken at Baseline in MG0003.	To be consistent with MG0003
5.1 Subject disposition	Added a table to summarize the number of participants at each visit by treatment group.	Based on DEM3 comment to understand the pattern of dropouts
6.1 Demographics	Age was changed to be the age at the time of MG0003 entry.	To compare age population across MG studies
6.1 Demographics	Added race, ethnicity group and needed rescue therapies in the observation period of MG0003 and entered MG0004	To be consistent with MG0003 and MG0007

6.2 Other Baseline characteristics	Defined MG-ADL cutoff as 5	The cutoff was determined in MG0003
6.4 Prior and concomitant medications	Added definitions of rescue medications	To provide clear definitions of rescue medications in programming
8.2 Adverse events	Reorganized adverse event summaries	To be consistent with MG0003
8.3.1 Potential drug-induced liver injury	Modified PDILI criteria and added new summaries	To be consistent with PSAP
8.4.2 Electrocardiograms	Removed QTcB	QTcB is not of interest
8.4.3.2 Suicidal risk monitoring	Suicidal risk monitoring summary analysis was removed	Listing is enough to provide all information
9.1.1 MG-ADL score	Added COVID-19 free analysis for MG-ADL summary. Added MG-ADL (excluding ocular items) summary.	To evaluate impact of COVID-19 pandemic. To be consistent with MG0003.
9.1.2 MG-C score	Added by MuSK+ or AChR+ summary of MG-C score	Missing from last version
9.1.3 QMG scale	Changed subgroup analysis by MuSK+ or AChR+ only	Other subgroups are not needed
9.2.5 MG-ADL responder rate (≥ 2.0 points improvement from Baseline)	Removed summary for imputed values and changed the summary for all visits instead of first 6 weeks	NRI imputation is not applicable to MG0004.
9.2.6 QMG responder rate (≥ 3.0 points improvement from Baseline)	Removed summary for imputed values and changed the summary for all visits instead of first 6 weeks	NRI imputation is not applicable to MG0004.
9.2.7 MG-C responder rate (≥ 5.0 points improvement from Baseline)	Removed summary for imputed values and changed the summary for all visits instead of first 6 weeks	NRI imputation is not applicable to MG0004.
10 PHARMACOKINETICS AND PHARMACODYNAMICS	Updated ADA participant categories and related summary analysis	To be consistent with MG0003

11.2 Specific analyses for Pharmaceuticals and Medical Devices Agency (PMDA)	Updated AE summaries based on changes in Section 8.2	To be consistent with AE summaries on all participants
11.3 Headache questionnaire	Added text in SAP for headache listing in shells	To be consistent with shells
11.4 Myasthenia Gravis Foundation of America (MGFA) by Visit	Added MGFA listing to SAP	To include MGFA data
13.7 Markedly abnormal laboratory and diagnostic criteria for Rozanolixizumab program	Added corrected calcium algorithm and updated the marked abnormality criteria for corrected calcium and eGFR formula parameters.	For clarity
13.8 AEs of focus for Rozanolixizumab program	Updated definitions of AEOF	To be consistent across MG studies

This document cannot be used to support any marketing authorization application and any extensions or variations thereof.

STATISTICAL ANALYSIS PLAN SIGNATURE PAGE

This document has been reviewed and approved per the Review and Approval of Clinical Documents Standard Operating Procedures. Signatures indicate that the final version of the Statistical Analysis Plan (SAP) or amended SAP is released for execution.

PUBLIC COPY
This document cannot be used to support any marketing authorization application and any extensions or variations thereof.
